**Stopping Rules**

We believe this trial conveys minimal risk. It is unlikely that any new information will become available during this trial that would necessitate stopping the trial.

### III. Subject Participation

**A. Recruitment**

We will recruit adults through the KU Weight Management clinic at KU Medical Center. Adults are primarily referred to the clinic via KU Health System physicians and contacted via phone or HIPAA-compliant messaging in their medical record to schedule an initial appointment with a clinic physician. The physician will conduct a comprehensive evaluation of the patient health status, including pertinent medical history. A study coordinator will assist with explaining a basic overview of intervention components in-person to evaluate initial interest. If interested, potential participants will participate in group Zoom® sessions with a study coordinator to obtain consent.

**B. Screening Interview/Questionnaire:**

The pre-screening for ability to participate in moderate to vigorous exercise and follow the diet prescription will be completed in the initial appointment with the clinic physician. Following the physician appointment, participants will be screened for other eligibility (e.g., commitment to study components, access to wifi) by a study coordinator.

**C. Informed Consent Process And Timing Of Obtaining Of Consent**

[name] will obtain written informed consent. Remote video chat sessions (Zoom) will be scheduled with participants who are deemed to be initially eligible to participate. This video chat session will provide an opportunity to describe the project in detail, answer questions, verify eligibility, and to obtain consent and assent. Prior to the consenting session, the participant will be sent the consent form and cover letter through The University of Kansas Medical Center's (KUMC) secure email system. The study team will use the "share screen" option on Zoom to walk through each section of the consent document while noting questions that arise and answering these questions fully. Participants who are willing to participate in the study will sign and date the consent and/or assent forms electronically via REDCap.

Participants/caregivers will be given unlimited time to make the decision on whether to participate. The study team member who conducted the consent meeting will also sign and date after reviewing the signed consent forms and verifying completeness. Study staff will provide the participant with a fully signed consent form for their records.

**D. Alternatives to Participation**

Participants may join other weight management programs.

**E. Costs to Subjects**

There will be no costs to the participant or their family for this study.

**F. How New Information Will Be Conveyed To The Study Subject And How It Will Be Documented**

New information will be told to the participants before, during, or after their participation in the study by email that will be sent to all participants.

**G. Payment, Including a Prorated Plan for Payment**

Participants will not receive any payment for their participation in the study.

**H. Payment for a Research-Related Injury**

There will not be any payment for a research-related injury.

**IV. Data Collection and Protection**

**A. Data Management and Security:** Data base creation and management will be performed by experienced research staff. Research staff that enters data will be supervised and will be blinded to condition. The PI and study coordinator will have access to study data. We have extensive experience in data entry, data checking, and quality control from previous and current projects. The primary database will be maintained through KUMC's Redcap. Additional data (Fitbit Data) will be maintained a KUMC P-Drive. Prior to transfer of data files to non-study personnel (i.e., for statistical analysis), the files will be de-identified. Data will be categorized and entered into separate tables within a database, all linked by participant number. All key personnel have current Human Subjects/HIPPA certificates. Physical files will be stored in a locked file cabinet, in a locked office, in our space in the KUMC endowment building suite 100.

**B. Procedures to Protect Subject Confidentiality**

Confidentiality for participants may be at risk during data collection, entry, and storage. However, we will use a secure, HIPAA compliant system (i.e., REDCap) to serve as the study database to store all the demographic information that may lead to subject identification. The output from the Fitbit will be stored in the KUMC protected drive and only identified by a unique participation identification number to maintain confidentiality. All paper records will be kept in a locked file cabinet and information will not be released without written permission of the participant, except as necessary for monitoring by the KUMC IRB

**C. Quality Assurance / Monitoring:** At logical time points, the data will be checked for outliers and normalcy. Questionable data (e.g.,  $>3$  standard deviations from the mean) will be re-checked for accuracy and re-entered if necessary.

**V. Data Analysis and Reporting**

**A. Statistical and Data Analysis**

The effectiveness of the intervention will be assessed by estimating a confidence interval for weight loss percent at 3 months. If the 95% CI includes 5% and the observed weight loss exceeds 2.5%, we will consider that the clinical effectiveness of the intervention is plausible and will seek to confirm this in a larger trial. We evaluated the operating characteristics of this decision rule through simulation with  $n = 36$  and assuming 15% attrition. When the true weight loss percentage is at least 5% we will have a 97.5% probability of proceeding, while if the true weight loss was not clinically significant, e.g., weight loss of 4% or 2.5% we would have a 57% and 1% chance of proceeding respectively. This will ensure that we do not proceed when the true effectiveness is much less than has been determined clinically relevant. We will compare our observed recruitment, attendance, and adherence to observed values from our traditional weight management program ( $88 \pm 5\%$  recruitment,  $75 \pm 8\%$  attendance,  $80 \pm 3\%$  adherence) and previous studies utilizing the same diet plan, we expect to see similar rates in this intervention and will evaluate any characteristics of this trial which led to lower than expected rates for potential modification for a follow-up trial. The recruitment goal is set at 30 participants to account for 10-15% attrition and statistical analysis of a sample size of at least 24 participants. All statistical analyses will be conducted using SAS software version 9.4 or higher with a significance level set at 0.05.

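### The go/no-go rule requires the 95% CI to include 5%, so a CI wholly above 5% fails it, and the stated 97.5% chance of proceeding cannot be reached under the rule as written

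*Combined protocol and SAP*

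**What the plan says.** Section V.A (Statistical and Data Analysis) assesses effectiveness by "estimating a confidence interval for weight loss percent at 3 months". The condition for going on to a larger trial is "If the 95% CI includes 5% and the observed weight loss exceeds 2.5%, we will consider that the clinical effectiveness of the intervention is plausible". Both parts must hold.

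The section then reports a simulation of this rule with n = 36, "assuming 15% attrition". It gives three results: "When the true weight loss percentage is at least 5% we will have a 97.5% probability of proceeding", and, for smaller true effects, "weight loss of 4% or 2.5% we would have a 57% and 1% chance of proceeding respectively".

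Neither Section V.A nor any other section says what happens if the whole interval lies above 5%. Section V.B says only that the study should show whether to apply for funding for a larger trial. The SD of percent weight loss is not stated, nor is the sidedness of the interval. The general statement is that analyses are done "with a significance level set at 0.05".

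**The concern.** An interval can miss 5% in two ways: it can lie wholly below or wholly above. Missing below is evidence that the programme falls short of the benchmark. Missing above is evidence that it beats it. The written condition treats the two alike. An interval of 5.8% to 8.2%, for example, does not include 5% and so fails.

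The stated operating characteristics point to a different rule. A chance of proceeding that stays at 97.5% or more for every true loss from 5% upwards needs a rule that becomes easier to pass as the effect grows. The written one becomes harder.

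This is the only numerical effectiveness criterion in the document, and it feeds the decision to seek a larger trial. If the programme works well, the team must either report that its pre-specified criterion was not met or depart from it after seeing the data.

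**Working it through.** **Inputs from Section V.A**
- Proceed if the 95% CI includes 5% and the observed loss exceeds 2.5%.
- Simulated n = 36 with 15% attrition: 36 × 0.85 = 30.6, so 30 or 31 completers.
- Claimed probability of proceeding: 97.5% at a true loss of 5% or more, 57% at 4%, 1% at 2.5%.
- Recruitment goal 30: 30 × 0.85 = 25.5, so about 26 completers.

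**Assumptions**
- A two-sided one-sample t interval, mean ± t(0.975, n−1) × s/√n, with normally distributed percent loss.
- SD not stated, so it is back-solved below and then varied.

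**Step 1: what can be said without an SD.** At a true loss μ = 5%, P(lower limit ≤ 5 ≤ upper limit) = 0.95 by construction. Adding the 2.5% condition can only reduce this. The written rule is therefore capped at 95% there, for any n and SD. By contrast, P(upper limit ≥ 5) = 1 − 0.025 = 0.975 at μ = 5%, which is the plan's figure whenever the 2.5% condition has negligible effect. Reading the interval as a one-sided 95% upper bound does not help, since that gives 0.95 again.

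**Step 2: recover the SD and reproduce the plan's figures.** Let δ = (μ − 5)√n/SD and let T be noncentral t with n−1 degrees of freedom and noncentrality δ. Then P(upper limit ≥ 5) = P(T ≥ −t(0.975, n−1)). Setting this to 0.57 at μ = 4 gives SD = 2.97 with 30 completers and 3.02 with 31. With n = 31 and SD = 3.02, the standard error is 3.02/√31 = 0.542, t(0.975, 30) = 2.042, and a typical half-width is 2.042 × 0.542 = 1.11 points.

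The upper-limit rule, with the 2.5% condition kept, then gives:

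| True loss | Plan states | Upper-limit rule |
|---|---|---|
| 5% | 97.5% | 97.5% |
| 4% | 57% | 57% |
| 2.5% | 1% | 0.6% |

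All three agree to the plan's rounding. The 57% was used to set the SD, so the independent checks are the 97.5% and the 1%.

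**Step 3: the rule as written.** P(CI includes 5) = P(−t ≤ T ≤ t), together with observed loss above 2.5%. Simulation with 1,000,000 draws per scenario, n = 31, SD 3.02:

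| True loss | As written | Upper-limit rule |
|---|---|---|
| 5% | 95.0% | 97.5% |
| 5.5% | 85.5% | 99.8% |
| 6% | 57% | >99.9% |
| 7% | 5.4% | >99.9% |
| 8% | 0.04% | >99.9% |

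As a rough check at μ = 6: the interval clears 5% once the observed mean passes about 5 + 1.11 = 6.11, so somewhat more than half of trials still include 5%.

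The written rule is symmetric about 5% apart from the 2.5% condition. A true loss of 6% therefore has the same 57% chance of proceeding as a true loss of 4%, which the plan itself calls not clinically significant.

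**Step 4: sensitivity.** With 26 completers and SD 3.0, the written rule gives 95%, 87%, 63%, 10% and 0.2% at true losses of 5%, 5.5%, 6%, 7% and 8%. With 26 completers at a true loss of 7%, it gives 31% with SD 4 and 50% with SD 5. These larger SDs do not fit the plan's other figures (at a true 4% they give 77% and 83–84%), so they serve only as a range. For SDs from 2 to 6 with 31 completers, the maximum over true loss is about 95%, reached at 5%.

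**The case against.** The best defence is that this is a slip of wording. The plan never says that an interval above 5% means stop. It says its purpose is to avoid proceeding when the effect is much too small, and it describes a high chance of proceeding for all losses of 5% or more. Under the apparent intended rule, 97.5% is correct at 5% and conservative above it, so the simulation itself need not be wrong. No sensible team would abandon a programme because it did too well. The study is also a single-arm feasibility pilot: the rule touches no participant, and recruitment, attendance and adherence are considered as well.

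Most of this is fair. The intent is probably as described, and the 97.5% is an error only relative to the rule as worded. But a pre-specified criterion should be the one that was simulated, and the section attributes its figures to the rule it has just written. An interval above 5% fails the only stated condition, and the plan offers no other route. Nor is the discrepancy limited to the 2.5 points at exactly 5%; it grows quickly above that.

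Two cautions on the figures also stand. The SD is inferred, and it is calibrated to 30 or 31 completers, so the 26-completer results are a sensitivity case. The direction is the same in every case tried.

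**Conclusion.** The concern holds. The written rule and its stated operating characteristics contradict each other. For a two-sided interval, the rule cannot exceed 95% at a true loss of 5%, a conclusion that needs neither the SD nor the sample size. How fast it falls above 5% does depend on the assumed SD. Matched to the plan's own simulation (31 completers, SD 3.02), it is 57% at 6% and 5.4% at 7%, where the upper-limit rule exceeds 99.9%. That the simulation used the upper limit alone is an inference, though a strong one. This should be corrected before the 3-month data are seen, because the literal rule reverses the decision when the intervention works well.

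**What to change.** In Section V.A, replace the requirement that the 95% CI include 5% with: the upper limit of the two-sided 95% CI for percent weight loss is at or above 5%. Keep the condition that the observed loss exceeds 2.5%. An interval wholly above 5% then counts as proceed, and the stated 97.5% becomes right at 5% and a lower bound above it.

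The cost is one sentence, with no added participants, data or analyses. The author of the simulation should confirm that this is the rule that was run, and the SD used should be stated.

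The rewording does not settle a separate mismatch. The 57% and 1% belong to n = 36, whereas "The recruitment goal is set at 30 participants to account for 10-15% attrition and statistical analysis of a sample size of at least 24 participants". With 24 analysed and SD 3, they become about 65% and 2.6%, so those two figures should be restated for the sample actually planned.

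### The stated chances of proceeding (97.5%, 57%, 1%) belong to about 31 analysed participants and an unstated SD near 3, not to the planned 24-26, and for true losses below 5% the rule loosens as the interval widens

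*Combined protocol and SAP*

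**What the plan says.** Section V.A (Statistical and Data Analysis) judges effectiveness by "estimating a confidence interval for weight loss percent at 3 months". The team treats clinical effectiveness as plausible, and seeks a confirmatory trial, "If the 95% CI includes 5% and the observed weight loss exceeds 2.5" percent.

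The rule's behaviour was simulated with n = 36 "and assuming 15% attrition". The results given are: "When the true weight loss percentage is at least 5% we will have a 97.5% probability of proceeding", and for losses the plan calls not clinically significant, "weight loss of 4% or 2.5% we would have a 57% and 1% chance of proceeding respectively". The section then concludes: "This will ensure that we do not proceed when the true effectiveness is much less than has been determined clinically relevant".

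Later in the same section the trial's size is set differently: "The recruitment goal is set at 30 participants to account for 10-15% attrition and statistical analysis of a sample size of at least 24 participants". No SD for percent weight loss appears anywhere in the document, and the three probabilities come with no sensitivity range.

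**The concern.** For a true loss below 5%, the interval contains 5% essentially when its upper limit reaches 5%. The observed mean needed to proceed is then 5 minus the half-width of the interval. More variable data, or fewer people analysed, widen the interval and lower that bar. Poor retention, itself a feasibility problem, would make a favourable decision more likely.

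Two things follow. The quoted probabilities describe a larger trial than the one planned. And the sentence of assurance is offered as a property of the rule, when it depends on an SD that the reader is not given. What is at stake is the decision to seek funding for a larger trial (Sections V.A and V.B), for which the plan gives no other numerical go/no-go rule.

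**Working it through.** **Inputs.** From Section V.A: two-sided 95% CI, target 5%, floor 2.5% on the observed mean, 36 enrolled with 15% attrition in the simulation, 30 recruited and at least 24 analysed in the plan. Assumed: normally distributed percent loss and a t-based interval. The SD is not stated and is back-solved below.

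**Rule as simulated.** With mean m, sample SD s and n analysed, the half-width is h = t(0.975, n-1) × s/√n. Proceed if m + h ≥ 5 and m > 2.5. With s at its assumed value, the cut-off on m is 5 - h.

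**Step 1: reproduce the plan's figures.** 36 × 0.85 = 30.6, about 31 analysed. At SD 3, h = 2.042 × 3/√31 = 1.10, so the cut-off is 3.90. Simulation (200,000 or more draws per setting) compares as follows:

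| n = 31 | True 5% | True 4% | True 2.5% |
|---|---|---|---|
| Plan states | 97.5% | 57% | 1% |
| SD 2 | 97.5% | 23% | 0% |
| SD 3 | 97.5% | 56% | 0.6% |
| SD 4 | 97.5% | 73% | 8% |

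Only an SD of about 3 fits all three. Treating attrition as random gives 97.5%, 56.9% and 0.7% at SD 3. A z-based interval needs an SD of about 3.1.

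**Step 2: which reading gives 97.5%.** Taken literally, an interval that includes 5% must also have its lower limit at or below 5%. That gives 95.0% at a true 5%. At a true 7% (n = 31, SD 3) it gives only about 5%, because the whole interval usually lies above 5%. The stated 97.5% for losses of at least 5% matches only the upper-limit reading.

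**Step 3: the planned size.** 30 × 0.85 = 25.5, so 25 or 26 analysed, with 24 as the stated minimum. At SD 3 the cut-off is 5 - 2.060 × 3/√26 = 3.79 for n = 26, and 5 - 2.069 × 3/√24 = 3.73 for n = 24. The chances become 97.5%, 63-65% and 1.7-2.6%. (At the plan's lower attrition of 10%, 27 would remain, and the figures would lie between those for 26 and 31.)

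**Step 4: a larger SD (assumed values).**

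| SD | True 4%, n = 26 | True 2.5%, n = 26 | True 2.5%, n = 24 |
|---|---|---|---|
| 3 | 63% | 1.7% | 2.6% |
| 4 | 77% | 14% | 17% |
| 5 | 84% | 31% | 34-35% |
| 6 | 86% | 44% | 45% |

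At a true 5% the chance stays near 97.5% throughout, so the loosening concerns true losses below 5%.

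**Step 5: more dropout, SD held at 3.** Going from 31 to 24 to 15 analysed, the chance at a true 2.5% rises from 0.6% to 2.6% to 15%. Fifteen analysed would be half of 30, well outside the planned attrition.

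**Step 6: the 2.5% floor.** It can bind only when h exceeds 2.5, that is when s > 2.5 × √n / t. This is 6.8 at n = 31, 6.2 at n = 26 and 5.9 at n = 24. At SD 3 it changes nothing. With much noisier data it caps the chance at a true 2.5% near 50%, since the observed mean then exceeds 2.5% half the time.

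**The case against.** The strongest reply is that the large figures lie outside the plan. The only SD recoverable from the document is about 3. At that value, moving to the planned size raises the chance at a true 2.5% only to 1.7-2.6%, which is a small practical harm. That stands. A reader might infer that this trial has a 31-44% chance of a false go. The document does not support that, because SDs of 4-6 are assumptions, as is a loss of half the participants. Attrition over 24 weeks also need not equal missing weights at 3 months, since the schedule of evaluations lists anthropometrics weekly.

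A reader might also take the non-binding floor for a mistake. It is a backstop for imprecise data: at n = 15, SD 6 and a true 2.5% it cuts the chance of proceeding from 68% to 49%.

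The consequence is limited too. Passing leads to a larger confirmatory trial, not to an efficacy claim, and a small single-arm pilot may reasonably favour sensitivity. The plan openly reports a 57% chance at a true 4%. Recruitment, attendance and adherence are benchmarked in Section V.A, and failure to recruit or deliver the intervention is a stop trigger in Section II.H. Retention, however, has no threshold of its own.

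None of this answers the narrower point: the quoted probabilities are for a different n, the SD behind them is not given, and the assurance is worded without condition.

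**Conclusion.** The point holds in a limited form. The three stated probabilities are reproducible, so the simulation itself is not in doubt, but they are not those of the planned trial. At the implied SD and the planned size, the main change is at a true 4% (57% becomes 63-65%), with a small rise at 2.5%. For true losses below 5% the rule loosens as the interval widens, so the assurance is conditional: it is sound if the SD is about 3 or less, and fails progressively above that. An SD below 3 makes false proceeding rarer still, so the stated protection is not confined to one exact value.

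This rests on normality, a t-based interval and the upper-limit reading of the rule. The SD of 3 is inferred from agreement with all three stated figures. The document gives no basis for saying that the actual SD will be larger, and none for ruling it out.

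**What to change.** In Section V.A:

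1. State the SD of percent weight loss used in the simulation and where it comes from.
2. Restate the three probabilities at 24-26 analysed over a range of SDs, for example 3 to 6.
3. Replace the sentence of assurance ("This will ensure that we do not proceed when the true effectiveness is much less than has been determined clinically relevant") with those figures.
4. Apply the rule only if the plan's own minimum of 24 participants is analysed.
5. Word the first condition as the upper 95% limit being at least 5%, the reading that yields the stated 97.5%.

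The cost is a re-run of an existing simulation and a few sentences.

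Raising the minimum observed loss to about 3.9%, the cut-off implied by n = 31 and SD 3, is an option for the sponsor to weigh and not a required correction. At n = 26 and SD 5 it would cut the chance of proceeding at a true 2.5% from 31% to about 7.6%. It would also lower the chance at a true 5% to about 87% (SD 5) or 82.5% (SD 6). The value is itself derived from an n that is not the planned one, and a true 4% would still proceed a little over half the time.

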### **B. Study Type and Design**

This study is a 24-week, single-arm trial investigating the feasibility of a flipped classroom behavioral intervention for weight management. We will recruit up to 30 adults ages 18+ with a body mass index greater than or equal to 25 kg/m^2 to participate in weekly, 1-hour group weight management education delivered remotely via Zoom with a trained health educator. Participants will receive a dietary prescription of 1200-1500 calories/day (5 portion-controlled meals and 5+ servings of fruits and vegetables) and exercise prescription of 150-300 minutes exercise/week. Additionally, participants will be asked to self-monitor diet and exercise adherence weekly. Feasibility outcomes will be collected at baseline, 12-weeks, and 24-weeks.

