### **D. Specific methods and techniques used throughout the study**

#### **1. Intervention:**

*Virtual, group instruction:* Participants will be complete a total of 24, 1-hour group education sessions with a trained health educator. The group size will be 15-18 participants with continuous recruitment until reaching a total of 30 participants. Sessions will be delivered virtually (Zoom®). Prior to each group meeting, participants will be provided hard copy and audio/visual versions (podcasts and YouTube®) of the lesson to be covered in the upcoming meeting. group session will follow a pre-determined structure: group discussion, review of adherence, 5 to 10 minutes of physical activity, and an active learning-based education. Thus, active learning-based education will include: case vignettes, group debates/discussions, think-pair-share activities, gamification of health-related topics, creation of meal and physical activity, problem-solving barriers to a healthy diet and physical activity, and hands-on worksheets.

- i. Diet Prescription. Participants will receive a diet prescription of 1200-1500 kilocalories (kcals), consisting of 5 portion-controlled meals [(PCMs); 3 shakes and 2 entrees], 5 servings of fruits and vegetables, and zero-calorie beverages. All PCM shakes will be prescribed from the company Health Management Resources (HMR), consisting of 100 kcals and 10g of protein/shake. PCM entrees are available either via HMR or approved outside entrees for purchase at the grocery store as determined by the RD. Guidelines for the approved outside entrees are <300 kcals, <10g sugar, and <3g saturated fat per PCM. Participants will be encouraged to consume at least 65 ounces of zero-calorie beverages per day. Adherence to the diet prescription will be monitored via weekly self-monitoring sheets submitted to the RD by email prior to the educational session for review and feedback.
- ii. Exercise Prescription. Participants will be asked to engage in 45 minutes of moderate- to-vigorous exercise 5 days per week or 50,000 steps per week. A pedometer will be available for purchase if desired, but participants may use personal step counting devices (e.g.,

phone apps, watches). Adherence to the prescribed MVPA and steps will be assessed using weekly self-monitoring sheets submitted to the RD via email prior to each session.

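### The quoted chances of proceeding come from a simulation of 36 enrolled, but the trial enrols at most 30, so the false-go rates are understated

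*Combined protocol and SAP*

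**What the plan says.** Section V.A (Statistical and Data Analysis) gives a decision rule for going on to a larger trial: "If the 95% CI includes 5% and the observed weight loss exceeds 2.5" per cent, effectiveness is regarded as plausible. The chances of proceeding under this rule were obtained by "simulation with $n = 36$ and assuming 15% attrition". They are given as 97.5% when the true loss is at least 5%, and for smaller effects as "weight loss of 4% or 2.5% we would have a 57% and 1% chance of proceeding respectively". The section concludes that the rule protects against proceeding when the true effect is far below clinical relevance.

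The enrolment figure is different. Section II.B (Study Type and Design) says "We will recruit up to 30 adults ages 18" and over. Section II.D.1 (Intervention) describes "continuous recruitment until reaching a total of 30 participants". Section V.A itself says "The recruitment goal is set at 30 participants to account for 10-15% attrition and statistical analysis of a sample size of at least 24 participants". The plan does not explain the step from 36 to 30, gives no operating characteristics for 30, and states no SD for percent weight loss.

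**The concern.** The simulated trial and the planned trial are not the same size. Under this rule a smaller sample errs in the permissive direction. The rule asks whether the interval reaches 5%, so imprecision helps an inadequate effect to pass. If fewer people are analysed than were simulated, the true chances of proceeding at 4% and 2.5% are higher than stated.

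Those two figures are the plan's only evidence that the rule screens out weak effects. Section V.B makes the decision on seeking external funding a main outcome of the study, so they should describe the study that will be run.

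**Working it through.** **Inputs.** From section V.A: 36 simulated, 15% attrition; recruitment goal 30, attrition 10-15%, at least 24 analysed; stated chances of proceeding 97.5%, 57% and 1%. From sections II.B and II.D.1: 30 enrolled. The SD of percent weight loss is not in the documents and is an assumption here.

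**Numbers analysed.**
- Simulated: 36 × 0.85 = 30.6, so 30 or 31.
- Planned: 30 × 0.85 = 25.5 and 30 × 0.90 = 27.
- Floor: 24/30 = 0.80, which is 20% attrition.

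The 30 cannot be read as 36 less dropouts, because the plan calls it the recruitment goal and takes attrition from it.

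**Formula.** For n analysed, true mean loss μ and SD σ, with a normal outcome and a t-based interval:

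P(proceed) = P( x̄ + t(0.975, n−1) · s/√n ≥ 5 and x̄ > 2.5 ), averaged over the sampling distribution of s.

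This is the upper-limit form of the rule. Read literally (5% lies inside the interval), the rule gives 95% at a true 5%, not 97.5%, so the plan's 97.5% fits only the upper-limit form. At 4% and 2.5% the two forms agree to within about 0.02 percentage points.

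**Reproducing the plan's figures.** Solving for the SD that gives 57% at a true 4%:
- 30 analysed: SD 2.97
- 31 analysed: SD 3.02

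The same SD gives 97.5% at a true 5% and 0.6% at a true 2.5% (stated as 1%). One SD of about 3.0 with 30 or 31 analysed therefore fits all three published figures. This is consistency under an assumed SD, not a full reproduction.

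**The planned size, at SD 3.0.**

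| Analysed | True 5% | True 4% | True 3% | True 2.5% |
|---|---|---|---|---|
| 31 (simulated) | 97.5% | 56.5% | 5.1% | 0.6% |
| 30 (simulated) | 97.5% | 57.7% | 5.8% | 0.7% |
| 27 (10% attrition) | 97.5% | 61.5% | 8.5% | 1.4% |
| 26 (15% attrition) | 97.5% | 62.8% | 9.6% | 1.7% |
| 25 (15% attrition) | 97.5% | 64.1% | 10.8% | 2.1% |
| 24 (stated minimum) | 97.5% | 65.4% | 12.2% | 2.6% |

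The mechanism shows in the interval's half-width, taking s = 3.0. With 31 analysed it is 2.042 × 3.0/√31 = 1.10, so an observed loss of 3.90% is enough to proceed. With 24 it is 2.069 × 3.0/√24 = 1.27, so 3.73% is enough.

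**Sensitivity.**
- Random rather than fixed attrition, SD 3.1: 59.3% and 1.0% (true 4% and 2.5%) with 36 enrolled, against 65.5% and 2.8% with 30 enrolled.
- If 36 was the number analysed, the back-solved SD is 3.27, and 26 to 24 analysed gives 68-70% at a true 4% and 3.7-5.2% at a true 2.5%. The discrepancy is then larger.
- For 57% to be right with 25 or 26 analysed, the SD would have to be about 2.7.
- With SD 4 or 5 and 26 analysed, the chance at a true 2.5% is 14% or 31%. Most of that comes from the SD: with 30-31 analysed the same SDs already give 8-9% and 23-25%.

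**The case against.** The strongest reply is that little changes. Within the plan's own 10-15% attrition, the chance at a true 2.5% is about 1.4-2.1%, which hardly alters the claim about effects far below clinical relevance. At a true 4% the plan already admits to proceeding more often than not, and the 97.5% does not move. The largest values need 24 analysed, which is more attrition than the plan expects. The replacement figures rest on an SD recovered from one rounded percentage. The SD 4 and 5 results say more about the missing SD than about 36 versus 30. The study is a single-arm pilot, and no confirmatory claim depends on these numbers. Nor do the documents say which of 36 and 30 is out of date.

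Much of this stands. The shift is modest, its exact size is conditional on the SD, and the SD 4 and 5 figures are a reason to ask for the SD rather than a measure of this error. But none of it reconciles the two numbers. The direction holds for any SD compatible with the stated 57%. Every statement of enrolment in the plan says 30; the 36 appears only in the simulation. At a true loss of 3%, on which the plan is silent, the chance of proceeding roughly doubles between the simulated size and the stated minimum.

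**Conclusion.** The concern holds. The stated 57% and 1% belong to a trial with about 30-31 analysed, whereas this one will analyse about 25-27 and accepts 24. At SD 3.0, the chance of wrongly proceeding at a true 4% is 61.5-65.4%, which is 4.5 to 8.4 points above the stated 57%. At a true 2.5% it is 1.4-2.6%, against 0.6-0.7% at the simulated size.

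The mismatch in size needs no assumption. The amounts assume a normal outcome, a t-based interval, the upper-limit form of the rule and the back-solved SD. The correction should be made, but it does not overturn the design.

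**What to change.** Rerun the existing simulation with 30 enrolled and 10%, 15% and 20% attrition (27, 25-26 and 24 analysed). State the SD and its source, and write the decision rule in the form that was simulated. Replace the 57% and 1% with the new values, which will be about 61-65% and 1.4-2.6% if the SD is 3.0. Adding the result for a true 3% and for a larger SD would show how far the rule can be relied on.

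The recruitment target need not change. If 36 was in fact intended, sections II.B, II.D.1 and V.A must be brought into line with it instead.

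The cost is one rerun and an edit to a sentence or two, with no effect on participants or conduct. The reported false-go rates become slightly less favourable.
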